## **5. BASIC STUDY DESIGN**

This will be a multi-site, open label, prospective randomized trial involving ACS and stable CAD patients who come to the cardiac catheterization laboratory at Mayo Clinic, Mayo Clinic Health System (MCHS), and other U.S.A., and international sites.

Only ACS patients who come to the cardiac catheterization laboratory at the international sites, and both ACS and Non-ACS patients who come to the cardiac catheterization laboratory at Mayo Clinic, MCHS, and other U.S.A. sites will be considered for recruitment. The anticipated number of patients amongst the U.S.A. sites will be over 4,000 patients who undergo PCI per year and amongst the international sites, over 6,000 ACS patients who undergo PCI per year. Eligible, consented patients will undergo

randomization after PCI to either a conventional therapy arm or prospective genotyping arm. The conventional therapy arm patients will receive clopidogrel once daily after the index PCI and will be retrospectively genotyped for *CYP2C19*\*2, \*3 and \*17 alleles after completion of one year of treatment with clopidogrel. The prospective genotyping arm patients will be genotyped prospectively for *CYP2C19*\*2, \*3 and \*17 alleles and will receive treatment based on their genotype. In this group, patients who have the *CYP2C19* reduced function allele [i.e. \*2 allele (heterozygous or homozygous) or \*3 allele (heterozygous or homozygous)] patients will receive ticagrelor 90 mg bid. The WT *CYP2C19* patients will receive clopidogrel 75 mg once daily. If ticagrelor is discontinued prematurely in the reduced function *CYP2C19* allele patient due to intolerance and there is no contraindication for continued dual anti-platelet therapy, the patients and their physicians will be advised to substitute ticagrelor with prasugrel at 10 mg daily (5 mg in patients weighing less than 60 kg or age >75 years) or clopidogrel 150 mg daily.

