### **7.2 Randomization**

Patients will be randomized to one of two groups. The two arms are: the conventional therapy arm in which the patients will receive clopidogrel with retrospective genotype analysis performed at the end of one year of treatment, and the prospective genotyping arm, in which patients will have prospective genotyping performed to guide anti-platelet therapy. Patients in this group who are identified to have reduced function *CYP2C19* allele will receive ticagrelor and patients with WT *CYP2C19* allele will receive clopidogrel. Drug therapy with ticagrelor and clopidogrel will be given as per clinical guidelines. Both of these drugs are FDA approved and will be given for FDA approved indications for at least 12 months after index PCI. Ticagrelor will be administered at 90 mg twice daily, and clopidogrel will be administered at 75 mg daily. All patients will receive a standard loading dose of antiplatelet therapy per the individual institution's routine clinical guidelines (prior to PCI, during PCI, or first dose after PCI), i.e. clopidogrel 300-600 mg or ticagrelor 180 mg. If patients receive ticagrelor 180 mg as a loading dose, and are then assigned to receiving clopidogrel as maintenance therapy, a loading dose of clopidogrel 300-600 mg as per institutional preference will be recommended as the next scheduled dose and 75 mg once daily as subsequent maintenance dosing. Similarly, when a transition is made from clopidogrel to ticagrelor, those loaded with 300-600 mg clopidogrel and assigned to receiving ticagrelor will get as a next scheduled dose, ticagrelor 180 mg as a loading dose and will then receive 90 mg twice daily as maintenance therapy. Specific randomization-guided treatment (i.e. clopidogrel or genotype-guided ticagrelor) will commence within 72 hours after index PCI as soon as clinically possible. If ticagrelor is discontinued

prematurely in the reduced function *CYP2C19* allele patient due to intolerance and there is no contraindication for continued dual anti-platelet therapy, the patients and their physicians will be advised to substitute ticagrelor with prasugrel at 10 mg daily (5 mg in patients weighing less than 60 kg and age  $\geq 75$  years) or clopidogrel 150 mg daily.

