## **8.2 Informed Consent**

As a general guidance, patients will typically be approached when referred for coronary angiography in the outpatient or the inpatient setting or within 48 hours after index PCI. When a potential subject is identified, the study coordinator and/or site principal investigator (PI) will review the inclusion and exclusion criteria. If the patient is eligible, the study coordinator and/or PI will explain the study, review the consent form, answer questions, and if the patient is willing to participate, the consent form will be signed.

If the subject is consented prior to coronary angiography, the subject will then undergo coronary angiography as scheduled and only if PCI is performed and the patient requires at least one year of dual anti-platelet therapy, will the subject then be enrolled in the study, randomized, and begin anti-platelet drug therapy based on randomization to the conventional therapy arm or the prospective genotyping arm.

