## **10.2 Randomization Procedures**

After a subject has been consented, completed coronary angiography, and has met eligibility requirements, the subject will be randomized. Randomization will be performed using Medidata Balance. Subjects will be randomized at a 1:1 ratio to either 1) conventional therapy or 2) prospective genotyping with genotype-guided antiplatelet therapy (either clopidogrel or ticagrelor). Randomization will be stratified by age, sex, site, and CAD presentation (stable CAD, unstable angina/NSTEMI or STEMI).

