## 12. OUTCOME DETERMINATIONS

### 12.1 Primary Outcome

The primary outcome will be the time to occurrence of the composite endpoint of a major adverse cardiac event (MACE), i.e. non-fatal myocardial infarction, non-fatal stroke, CV mortality, severe recurrent ischemia, and stent thrombosis if not captured in other events, from the time of randomization through one-year of follow-up.

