#### Myocardial infarction

The diagnosis of myocardial infarction is dependent on whether it is *spontaneous*- or *procedure*- related:

- *Spontaneous*: Cardiac biomarkers (creatinine kinase-myocardial band, Troponin T or I) exceed the upper limit of normal according to the individual hospital's laboratory parameters or clinical presentation which is consistent or suggestive of ischemia.
- *Procedure-related excluding index PCI*:
  - In subjects with normal pre-procedural cardiac biomarkers, myocardial infarction within 24 hours post-PCI is indicated by cardiac biomarkers elevated above 3 times the upper limit of normal.
  - In subjects with elevated pre-procedural biomarkers, myocardial infarction within 24 hours post-PCI is indicated by cardiac biomarkers elevated above 3 times the upper limit of normal after biomarkers have exhibited a rise and fall indicative of completion of the presenting infarct.
  - MI greater than 24 hours post-PCI but prior to discharge is evidenced by any of the following:
    - a. A rise and fall in cardiac biomarkers (preferably troponin) with at least one of the values in the abnormal range for that laboratory, together with at least one of the developments listed below, is a manifestation of myocardial infarction. The abnormal range for your laboratory means levels above the 99th percentile of the upper reference limit (URL) for normal subjects.
      - i. Ischemic symptoms;
      - ii. ECG changes indicative of new ischemia (new ST-T changes, new left bundle branch block, or loss of R wave voltage);
      - iii. Development of pathological Q waves in 2 or more contiguous leads in the ECG (or equivalent findings for true posterior MI);
      - iv. Imaging evidence of new loss of viable myocardium or new regional wall motion abnormality;
      - v. Documentation in the medical record of the diagnosis of acute myocardial infarction based on the cardiac biomarker pattern in the absence of any items enumerated in 1-4 due to conditions that may mask their appearance (e.g. peri-operative infarct when the subject cannot report ischemic symptoms, baseline left bundle branch block, or ventricular pacing).
    - b. Imaging evidence of a region with new loss of viable myocardium at rest in

the absence of a non-ischemic cause. This can be manifested as:

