## 15.5 Specification of the Primary Analyses

Hypothesis 1A. The effect of genotype-guided antiplatelet therapy versus conventional care in patients with a reduced function *CYP2C19* allele will be estimated using a Cox proportional hazards regression model, with covariates including variables used for stratified randomization and other subject factors associated with MACE. The analysis will be conducted under the intention-to-treat principle, with follow-up beginning at randomization, but with genotype defined by the Taqman genotyping assay. Those whose prospectively defined genotype disagrees with their TaqMan-based genotype will nevertheless be analyzed based on the TaqMan result, which is the only result that is available in both arms. A sensitivity analysis will be done, taking into account the Spartan result. In the retrospective genotyping group, reduced function status will be determined by the TaqMan assay results at least one year after PCI. Subjects who withdraw or are lost during follow-up will be treated as censored at the date of last contact. Patients who complete follow-up at 12 months will be considered censored from that point onward. The proportional hazards assumption will be assessed visually using plots of scaled Schoenfeld residuals. A two-sided likelihood ratio test will be used to assess the significance of the partial effect of treatment; a p-value less than 0.05 will be considered statistically significant. Kaplan- Meier curves will be used to display survival free of MACE estimates over the first year of follow-up.

Hypothesis 1B. It is also important to determine the effect of genotype-guided antiplatelet therapy versus conventional care in patients with the wild type *CYP2C19* allele. In this case, both groups will be given clopidogrel, but the genotype-guided group patients and their physicians will know prospectively that they have the wild-type allele, at least based on the Spartan platform. The analysis will be done as outlined above in the LOF group, again defined by the TaqMan-based assessment of wild-type status. It is expected that the null hypothesis will prevail, but it is important to confirm that knowledge of genotype in and of itself does not have an effect on the rate of MACE events.

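### Both PCI rise-and-fall rules for MI exclude the index PCI, so in the days after randomization recurrent symptoms with a biomarker still raised from the presenting infarct can meet the definition of a new MI

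*Combined protocol and SAP*

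**What the plan says.** Section 12.1 counts MACE "from the time of randomization through one-year of follow-up", and Section 15.5 repeats that the analysis is by intention to treat "with follow-up beginning at randomization". Section 5 has "randomization after PCI to either a conventional therapy arm or prospective genotyping arm", Section 8.2 allows consent up to "within 48 hours after index PCI" as general guidance, and Section 7.2 says that randomized treatment "will commence within 72 hours after index PCI as soon as clinically possible". STEMI and NSTEMI patients are enrolled and form levels of a stratification factor (Section 10.2). Table 1 lists CK-MB, troponin and study endpoint events in the post-procedure column; the biomarkers come only from clinically indicated tests.

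Section 12.3 divides MI into two branches:

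- **Spontaneous.** A biomarker above the local upper limit of normal, or a clinical picture of ischemia. There is no rise and fall, no comparison with an earlier value and no minimum time after the index PCI.
- **"Procedure-related excluding index PCI".** Here sit the rule for patients with raised pre-procedural biomarkers, under which a new elevation counts only "after biomarkers have exhibited a rise and fall indicative of completion of the presenting infarct", and the rule for MI more than 24 hours after PCI but before discharge. The second has criterion (a), a rise and fall plus one of items i to v, and criterion (b), imaging evidence.

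Section 12.3 also states that the Adjudication Committee will use these definitions.

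**The concern.** A patient who presents with an infarct can be randomized while biomarkers from that infarct are still raised. If chest discomfort recurs in the following days and no new procedure is done, the rules written to separate a new infarct from the old one are out of scope by their heading. The rule that remains can be met by the old elevation.

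Severe recurrent ischemia does not intercept these cases, because it applies only when the MI criteria are not met. Probable stent thrombosis, which includes acute MI in the target-vessel territory without angiographic confirmation, could be affected in turn.

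At stake is the primary comparison in loss-of-function (LOF) carriers, which rests on few events (about 82 at the planned size). False events that occur about equally in both arms add to the count but dilute the hazard ratio. The MI and stent thrombosis component counts, which are exploratory outcomes, would be affected too.

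**Working it through.** **1. Which rule applies.** Randomization follows the index PCI and must precede randomized treatment, which starts within 72 hours of that PCI. That randomization falls inside 72 hours is an inference from the treatment window. The clock then runs. For an event with no further procedure:

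- Procedure-related branch: not applicable, because the index PCI is excluded.
- Spontaneous branch, 'or' as printed: a raised residual biomarker alone is enough.
- Spontaneous branch, 'or' read as 'and': a raised residual biomarker plus ischemic symptoms is enough.

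The gap therefore does not depend on the and/or question. The plan does use a baseline elsewhere: completion of the presenting infarct for a later PCI, and the closest pre-operative value for CABG.

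**2. Which episodes change the primary endpoint.** Severe recurrent ischemia is part of the same composite. It needs rest symptoms over 10 minutes that cause or prolong hospitalization, plus new ECG changes or urgent revascularization. An episode that meets this is a primary event under either label, and only the component count changes. An episode that does not meet it becomes a false primary event.

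**3. The plan's power figure.** Inputs are from Section 15.2.2, Tables 4 and 5, and Appendix C: HR 0.50, pooled LOF rate 4.5%, 5% dropout, 20% Korean share of further enrollment, n = 5270.

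- Korean patients: 1275 + 0.20 × (5270 − 4467) = 1436. North American: 3834.
- LOF: 1436 × 747/1275 + 3834 × 896/3192 = 841 + 1076 = 1917; × 0.95 = 1822.
- Events: 1822 × 0.045 = 82.
- Freedman: z = √82 × (1 − 0.5)/(1 + 0.5) = 3.02; power = Φ(3.02 − 1.96) = 85.5%, against the stated 85.8% (z = 3.031 in Appendix C).

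**4. Illustration of dilution.** With p_t = 1 − (1 − p_c)^0.5 and a mean of 4.5%, the arm rates are p_c = 5.97% and p_t = 3.03%. Add an assumed net false rate s to each arm:

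- HR = ln(1 − p_t − s) / ln(1 − p_c − s)
- Events = 1822 × (0.045 + s)
- z = 3.031 × (√events × |ln HR|) / (√82 × ln 2); power = Φ(z − 1.96)

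| s per arm (assumed) | False events | HR | Events | z | Power |
|---|---|---|---|---|---|
| 0 | 0 | 0.50 | 82 | 3.03 | 85.8% |
| 0.25% | 5 | 0.52 | 87 | 2.94 | 84% |
| 0.5% | 9 | 0.54 | 91 | 2.86 | 82% |
| 1% | 18 | 0.57 | 100 | 2.72 | 78% |
| 2% | 36 | 0.62 | 118 | 2.50 | 70% |

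Freedman's formula applied directly to the same rates agrees within 2 points.

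**5. If false events are already inside the 4.5%.** Take s = 0.5%. The true pooled rate is then 4.0% (5.31% vs 2.69%), and the observed rates are 5.81% vs 3.19%. HR = 0.542, with events still 82. z = 3.031 × 0.613/0.693 = 2.68 and power is about 76%.

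**The case against.** Several points on the other side have force.

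- **Many such episodes already count.** Correct: those that meet the severe recurrent ischemia criteria leave the hazard ratio unchanged. Only net false events matter, which is how s is defined above.
- **The rate is assumed.** Also correct. Section 15.2.2 reports an observed LOF rate of 4.8%, so any misclassified MIs are already in it, and the illustrated pooled rates of 5.0% to 6.5% lie above it. This undercuts the power figures as estimates. It does not show that the effect is small, since placing false events inside the 4.5% costs more power per event (step 5).
- **Filters exist.** A site must first suspect a MACE, and a blinded committee then reads the records; it may in practice discount a falling troponin. This makes misclassification less likely, but the committee is bound to the definition as written, and blinding to arm does not correct it.
- **The sub-rules may have been meant for the index admission.** Their references to the presenting infarct and to discharge suggest so, but the heading says otherwise. Early readmission would remain uncovered on either reading.

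A reader might also infer three stronger things that the documents do not support. First, that the trial's power has fallen to 78% or that its MIs are contaminated: the text shows that misclassification is possible, not that it has occurred. Second, that the false events are unrelated to treatment and equal by arm: this is an assumption. Some early symptoms in carriers on clopidogrel may be true reinfarction, and the trial is open label with sites referring events. Third, that they fall exactly where the genotype effect lies: Section 4 reports a difference over the first 30 days in one genetic substudy, not the first days, and says that it was not seen over 12 months.

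**Conclusion.** The gap is real. As written, for an early event with no new procedure, the MI definition does not separate a new infarct from the tail of the presenting one, whichever way the 'or' is read. This is a stated rule that misclassifies if followed, not merely missing detail, and it should be corrected.

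Its size is unknown. With net false events of 0.5% to 2% in each arm, the expected hazard ratio would be 0.54 to 0.62 and power about 82% to 70%; with few or none, the effect is near zero. These figures rest on an assumed rate, equal occurrence in both arms, a true hazard ratio of 0.50, and false events added on top of the 4.5% planning rate.

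**What to change.** In Section 12.3:

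1. Reconcile the procedure-related heading with the sub-rules beneath it, so that it is clear which rule governs the index admission.
2. Extend criterion (a): for subjects whose biomarkers were raised at index presentation and have not returned to normal, an MI requires evidence of a new rise from a stable or falling value, plus one of items i to v.
3. Where serial values are missing, let the blinded committee use criterion (b) or other listed evidence (ECG, imaging, angiography), so that true reinfarctions are not lost. This is needed because biomarkers come only from clinically indicated tests.
4. Assess episodes that do not qualify under severe recurrent ischemia.
5. Resolve 'or' versus 'and' in the spontaneous rule in the same edit.

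Apply the rule to all early MIs by blinded re-review of records already held. Because enrollment is well advanced, decide and date the change without reference to results by arm.

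The cost is one paragraph, matching adjudication instructions and a small re-review. The MI count, and so the observed event rate, may fall slightly. If the committee already works this way, the edit only documents its practice.

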### **Severe recurrent cardiac ischemia**

Recurrent cardiac ischemia and at least one of the following, but not fulfilling the criteria for MI:

- New or presumed new ischemic ECG changes (ST elevation  $\geq 1$  mm (0.1 mV) or ST depression  $\geq 0.5$  mm (0.05 mV), or T wave inversion  $\geq 1$  mm (0.1 mV) in at least 2 adjacent leads)
- Leading to urgent revascularization (PCI or CABG) unless not advised on reasoned grounds. Urgent revascularization (PCI or CABG) must occur during the same hospitalization as an in-patient episode of recurrent ischemia or be performed during the re-hospitalization resulting from an out-patient episode of recurrent myocardial ischemia. In countries where waiting lists for revascularization procedures exist, revascularization within 30 days of an episode of recurrent ischemia will qualify as urgent. For patients with a previous PCI, it will be recorded if revascularization is necessary for previously treated vessels (i.e. urgent target vessel revascularization) and any occurrences of stent thrombosis will be documented. PCI is defined as any attempt at revascularization even if not successful (e.g. angioplasty, atherectomy, or stenting).
- Other definitions:
  - Recurrent cardiac ischemia: Cardiac ischemic symptoms  $>10$  minutes at rest (started with exercise or spontaneously and did not resolve with rest), resulting in hospitalization if an outpatient, or prolongation of hospitalization if an inpatient but not fulfilling criteria for MI.
  - Cardiac ischemic symptoms: chest pain or discomfort or equivalent (e.g. neck or jaw symptoms, dyspnea believed to represent an angina pectoris equivalent) believed due to impaired coronary flow secondary to atherosclerotic disease.

### **Stent thrombosis**

Definite (presence of acute coronary syndrome with angiographic or autopsy evidence of thrombus or occlusion) or probable (unexplained deaths within 30 days after the procedure or acute myocardial infarction involving the target-vessel territory without angiographic confirmation).

### **Cerebrovascular accident (CVA)**

Loss of neurological function caused by an ischemic or hemorrhagic event with residual symptoms lasting at least 24 hours after onset or leading to death.

### **Transient ischemic attack (TIA)**

Loss of neurological function that was abrupt in onset but with complete return of function within 24 hours, presumed to be due to vascular etiology.

### **Bleeding**

All bleed events that require some form of intervention (e.g. doctor's visit, ER visit, hospitalization) will be captured, recorded, and classified as major, minor, or minimal.

- **Major bleeding**  
Symptomatic intracranial hemorrhage or clinically overt bleeding (including imaging) with a hemoglobin drop of  $\geq 5$  g/dL (adjusted for transfusion by 1 g/dL per unit of transfused blood).
- **Minor bleeding**  
Clinically overt bleeding (including imaging) with a hemoglobin drop of 3 to  $< 5$  g/dL (adjusted for transfusion by 1 g/dL per unit of transfused blood).
- **Minimal bleeding**  
Clinically overt bleeding (including imaging) with a hemoglobin drop of  $< 3$  g/dL (adjusted for transfusion by 1 g/dL per unit of transfused blood).

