### ***Ticagrelor***

Common adverse events include major and minor bleeding (8.7%), headache (6.5%), raised serum creatinine (7.4%), cough (4.9%), dyspnea (13.8%), atrial fibrillation (4.2%), and syncope (1.7%).

Ticagrelor may cause significant, sometimes fatal, bleeding. Hence patients with active pathological bleeding or history of intracranial hemorrhage, bleeding diathesis, and on chronic anticoagulation such as warfarin will be excluded.

Maintenance doses of aspirin above 100 mg reduce the effectiveness of ticagrelor; thus patients unable to take aspirin at 100 mg or less will be excluded.

In a randomized, double-blind study of patients with acute coronary syndrome, major bleeding events (not related to CABG) were reported in 4.5% of patients who received ticagrelor (n=9235) compared with 3.8% of patients who received clopidogrel (n=9186). Both were co-administered with aspirin and other standard therapy for 6 to 12 months. The bleeding episodes were fatal or life-threatening in 2.1% of ticagrelor-treated patients compared with 1.9% of clopidogrel-treated patients. Fatal events were reported in 0.2% of patients in each group. Fatal or life-threatening intracranial bleeding was reported in 0.3% and 0.2% of ticagrelor- and clopidogrel-treated patients, respectively. In a randomized, double-blind study of patients with acute coronary syndrome who underwent CABG surgery, major bleeding events were reported in 85.8% of patients who received ticagrelor (n=770) compared with 86.9% of patients who received clopidogrel (n=814). Both were co-administered with aspirin and other standard therapy for 6 to 12 months. The bleeding episodes were fatal/life-threatening in 48.1% of ticagrelor-treated

patients compared with 47.9% of clopidogrel-treated patients. Fatal bleeding events were reported in 0.9% and 1.1%, respectively, of patients.

If possible, minor bleeding should be managed without discontinuing ticagrelor therapy since therapy discontinuation increases the risk of myocardial infarction, stent thrombosis, and death. Although discontinuation increases the risk of subsequent adverse cardiovascular events, ticagrelor should be stopped 5 days prior to surgery, when possible. Hence if a surgical procedure is planned including CABG, surgery patients will be excluded since they will be unable to complete the 12-month duration of anti-platelet therapy.

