### 12.2 Secondary and Exploratory Pre-specified Outcomes

Secondary outcomes will include: The incidence of major or minor bleeding in subjects with reduced function *CYP2C19* allele(s) receiving ticagrelor versus clopidogrel.

Exploratory pre-specified outcomes include:

- The effect of *CYP2C19*\*17 genotype on bleeding risk, MACE, stroke, and CV survival.
- The effect of *CYP2C19*\*2 or \*3 genotype on multiple recurrent events (MACE, stroke, and CV survival) in the individual subject.
- Performing a pharmacoeconomic analysis of the conventional therapy approach as compared with the genotype-based approach in subjects who undergo PCI.
- Comparing the occurrence of MACE in subjects with reduced function *CYP2C19* allele(s) to those with WT genotype receiving clopidogrel.
- Comparing the occurrence of MACE in subjects with reduced function *CYP2C19* allele(s) receiving ticagrelor to those with WT genotype receiving clopidogrel.
- Assessing the effect of CAD presentation: a) Stable coronary artery disease; b) Unstable angina or NSTEMI; and c) STEMI on the effect of ticagrelor in subjects with reduced function *CYP2C19* allele(s) and on the association of *CYP2C19* genotype and occurrence of MACE.
- To assess the mechanism of coronary stent thrombosis in subjects with reduced function *CYP2C19* allele(s) receiving ticagrelor versus clopidogrel.
- To assess implementation of a CLIA-approved *CYP2C19* pharmacogenetic testing on the

Spartan platform (accuracy of genetic testing by sequence analysis, and genotype failure rates).

- Exploratory outcomes will also include the individual components of the primary outcome.
- To assess compliance with dual anti-platelet therapy by phone survey.
- To assess patients' attitudes towards genotyping and the results of genotyping.

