#### Cardiovascular death

Death from cardiovascular causes or cerebrovascular causes and any death without another known cause.

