### 15.2.3 Secondary Endpoint

To assess the incidence of major or minor bleeding not related to CABG. The PLATO trial observed a 1-year rate of major or minor bleeding of 14.6% in subjects receiving clopidogrel, and the genetic sub-study observed no significant decrease in major bleeding in those with loss-of-function alleles. Thus, assuming a 14.6% rate of major or minor bleeding at 12 months in reduced function subjects receiving clopidogrel, 1,694 subjects will provide 80% power if the bleeding rate in the ticagrelor group is at least 19.7%.

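### The bleeding definitions have no fatal category, so a fatal extracranial bleed with no hemoglobin value after onset, or a small drop, falls outside the major-or-minor bleeding endpoint

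*Combined protocol and SAP*

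**What the plan says.** Section 12.3 gives the definitions that the Adjudication Committee is to use. Bleeds that need some form of intervention "will be captured, recorded, and classified as major, minor, or minimal". The three classes are:

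- **Major:** "Symptomatic intracranial hemorrhage or clinically overt bleeding (including imaging) with a hemoglobin drop of" at least 5 g/dL.
- **Minor:** "Clinically overt bleeding (including imaging) with a hemoglobin drop of 3 to" below 5 g/dL.
- **Minimal:** overt bleeding with a drop below 3 g/dL.

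Each drop is adjusted by 1 g/dL per transfused unit. No class mentions death, and nothing says what to do when there is no hemoglobin value.

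The secondary endpoint in Section 12.2 is "The incidence of major or minor bleeding in subjects with reduced function" alleles, ticagrelor against clopidogrel. Section 15.2.3 adds a restriction: "To assess the incidence of major or minor bleeding not related to CABG". Minimal bleeding is not counted.

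The primary outcome in Section 12.1 is "non-fatal myocardial infarction, non-fatal stroke, CV mortality, severe recurrent ischemia, and stent thrombosis if not captured in other events". Section 12.3 defines cardiovascular death as "Death from cardiovascular causes or cerebrovascular causes and any death without another known cause". It does not say whether a fatal hemorrhage outside the brain is a cardiovascular cause.

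**The concern.** The worst possible result of a bleed does not affect how that bleed is classed. Two patients with the same fatal gastrointestinal hemorrhage could be counted differently according to whether a blood sample was taken after onset. If the bleed is also accepted as a known non-cardiovascular cause of death, the patient may appear in neither the efficacy nor the safety comparison.

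The plan has little else that would pick such a death up as an outcome. All-cause mortality is not listed among the outcomes in Sections 2.3, 12.1 or 12.2. Sections 14.2 and 14.4 say that known adverse events of the two drugs will not be recorded as study-related. Bleeding safety therefore rests mainly on this one endpoint. What is at stake is the credibility of the safety result, not the sample size.

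**Working it through.** **1. The plan's own bleeding figure.** Section 15.2.3 states 80% power for 14.6% against 19.7% with 1,694 subjects. Section 15.2 gives a two-sided 0.05 level and 1:1 allocation, so n = 847 per arm. With pooled variance under the null:

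z = [0.051 × √847 − 1.96 × √(2 × 0.1715 × 0.8285)] / √(0.146 × 0.854 + 0.197 × 0.803) = (1.484 − 1.045) / 0.532 = 0.826, which gives power 79.6%.

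The stated figure is reproduced.

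**2. How a fatal bleed is classed.** Applying Section 12.3 as written:

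| Fatal bleed | Bleeding class | In major-or-minor endpoint? | In MACE as cardiovascular death? |
|---|---|---|---|
| Symptomatic intracranial | Major, no hemoglobin value needed | Yes | Yes, as cerebrovascular death |
| Extracranial, drop at least 5 g/dL | Major | Yes | Not settled |
| Extracranial, drop 3 to below 5 g/dL | Minor | Yes, but not as major | Not settled |
| Extracranial, drop below 3 g/dL | Minimal | No | Not settled |
| Extracranial, no value after onset | None | No | Not settled |

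The last column is open because the cardiovascular death definition takes in deaths with no other known cause, and a documented extracranial bleed can be read as another known cause. The stent thrombosis definition does not help: its probable category takes only unexplained deaths within 30 days, or infarction in the target-vessel territory.

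**3. Expected number.** Section 7.6.2 reports, for bleeding not related to CABG in a large ACS trial: "Fatal events were reported in 0.2% of patients in each group". Carrying that rate over to this trial is an assumption.

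- Reduced-function subjects: 1,694 × 0.002 = 3.4 in total, or 847 × 0.002 = 1.7 per arm.
- Assumed range of 0.1% to 0.3%: 1.7 to 5.1 in total.
- All 5,270 randomized, relevant to the exploratory whole-arm bleeding comparison in Section 2.3: 5,270 × 0.002 = 10.5.

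These counts cover fatal bleeds of every site. Only those in the last two rows of the table are lost to the endpoint. The documents do not give that share, so at 0.2% the affected number lies between 0 and 3.4.

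**4. Effect on power.** Adding 0.2 percentage points to both rates (14.8% against 19.9%) in the formula of step 1 gives z = 0.813 and power 79.2%, a change of 0.4 points. As an extreme, taking 0.2 points from the ticagrelor rate alone gives 76.5%. That would require every fatal bleed on ticagrelor to be unclassified and none to be missed on clopidogrel.

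**The case against.** Much can be said for the plan, and several stronger readings do not survive it.

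- **A reader might infer that any fatal bleed without a hemoglobin drop is missed.** That is too broad. Symptomatic intracranial hemorrhage is major with no laboratory criterion. As a hemorrhagic stroke leading to death, it is also a cerebrovascular death. The same risk section gives fatal or life-threatening intracranial bleeding as 0.3% and 0.2%, so a good part of fatal bleeding may already be captured.
- **A reader might infer that these deaths are certainly outside MACE.** The text does not settle it. Blinded adjudicators could count a fatal bleed on antiplatelet therapy as cardiovascular; nothing requires or forbids this. Leaving clearly non-cardiovascular deaths out of MACE is an ordinary design choice.
- **A reader might infer that the gap can only favor ticagrelor,** because Section 3 says ticagrelor raises bleeding not related to CABG. What matters is how the unclassified fatal bleeds split by arm. Section 7.6.2 gives equal fatal rates, and among CABG patients 0.9% on ticagrelor against 1.1% on clopidogrel. With so few events, chance decides the sign.
- **The scenario is narrow.** Section 10.1 lists a complete blood count as usual baseline work, so one value after onset is normally enough to classify. The transfusion adjustment can also bring a heavily transfused patient to 5 g/dL.
- **The deaths are not lost to the record.** Sections 14.4 and 17.6.1 send every death to the blinded Adjudication Committee. The Operations Manual, which was not available for this review, may cover missing hemoglobin.

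These arguments limit the point but do not remove it. Adjudication makes the facts available, but the definition the committee must apply gives a fatal extracranial bleed no class of its own. When the drop is small, the written rule gives a definite and unsuitable answer, minimal.

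**Conclusion.** The point holds for fatal extracranial bleeds. With no hemoglobin value after onset the bleed has no class, and with an adjusted drop below 3 g/dL it is minimal. Both fall outside the secondary bleeding endpoint and may fall outside MACE. With a drop of 3 to below 5 g/dL it is counted, but only as minor.

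The size is small: 0 to about 3.4 subjects among 1,694. This assumes that the cited 0.2% applies here and leaves the affected share open. If the arms are affected equally, the change in power is about 0.4 points, which is negligible. The documents support no direction of bias. This is a gap in safety classification that is worth closing, not a threat to the primary analysis.

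**What to change.** 1. In Section 12.3, extend the major bleeding definition with: *or fatal bleeding (bleeding that directly results in death), regardless of hemoglobin value*.
2. In the cardiovascular death definition, state whether a fatal extracranial bleed counts as cardiovascular. Without this, the first change repairs the bleeding endpoint but leaves the MACE question open.

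The wording is short and no new data collection is planned, because deaths already go to adjudication. The real cost is procedural. Section 15.2.2 projects forward from about 3,900 enrolled, so this is a mid-trial change to an endpoint definition. It needs an amendment approved at each institution under Section 14.1, matching text in the adjudication documents, and a re-check, blinded to treatment, of deaths already adjudicated.
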